Title	Comparison of the ToFscan and TetraGraph during Recovery of Neuromuscular Function in the Post Anesthesia Care Unit
Running Title	ToFscan vs TetraGraph
Phase	N/A
Methodology	Randomized, Open-Label
Overall Study Duration	6 months
Subject Participation Duration	Less than 1 hour
Single or Multi-Site	Multicenter International
Objectives	The primary aim of this study is to assess the agreement and repeatability between TOF values obtained from ToFscan and TetraGraph
Number of Subjects	120 (40 per site)
Diagnosis and Main Inclusion Criteria	Patients undergoing an elective surgery and requiring administration of NMBA intraoperatively
Study Device	TetraGraph
Duration of Administration	Single stimulation of ulnar nerve repeated at specific intervals as outlined in the Study Procedures (Section 6.2)
Reference therapy	ToFscan
Statistical Methodology	This pilot study is meant to be descriptive and it aims to collect basic data for future larger study

4 Introduction

This document is a protocol for a human research study. This study will be carried out in accordance with the applicable United States government regulations and Mayo Clinic research policies and procedures.

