4.3 Risks and Benefits

- The benefits of using neuromuscular blockade monitoring devices:
Early detection of residual neuromuscular blockade
- The risks of using neuromuscular blockade monitoring devices:
Slight discomfort when electrical stimulation is administered

5 Study Objectives

Primary Objective

To assess the agreement and repeatability between TOF values obtained from the ToFscan and TetraGraph during recovery from neuromuscular blockade as measured upon arrival to the PACU, and then 5 (+5 min) and 10 (+10 min) minutes later.

Secondary Objective

Determine the incidence of postoperative residual weakness in the PACU (defined as TOFR <0.90).

Assess patient discomfort associated with each neurostimulation utilizing a verbal numeric rating scale (VNRS) from 0-10.

6 Study Design

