6.4 Primary Study Endpoints

The primary endpoint of the study will be the repeatability of values obtained by ToFscan and TetraGraph monitors.

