9.2 Visit 2 (Randomization and Treatment – day of surgery)

- Elective surgical procedure as per standard of care
- Intraoperative neuromuscular blockade, management, and neuromuscular antagonism will be at the discretion of the attending anesthesiologist.
- Upon arrival to the PACU, consenting patients will be randomized to have the TetraGraph placed on either their dominant or non-dominant arm. TetraGraph uses proprietary, single-use surface electrodes (TetraSens™, Senzime AB, Uppsala, Sweden) with stimulating electrodes placed over the ulnar nerve, a reference electrode placed on the adductor pollicis (1st digit) ([Figure 16.1](#)). The skin will be prepped with careful abrasion and cleansing of the skin in the usual fashion prior to electrode placement.
- ToFscan will be placed on the patient's opposite arm. Stimulating electrodes (Red Dot ECG electrodes, 3M, St. Paul, MN) will be placed over the ulnar nerve with the negative electrode near the wrist crease and positive electrode placed 3-4 cm proximally. The skin will be prepped with careful abrasion and cleansing of the skin in the usual fashion prior to electrode placement. The ToFscan utilizes a thumb splint with the encased transducer secured to the hand ([Figure 16.2](#)).
- To obtain measurements with TetraGraph, TOF stimulation will be performed at 50mA and the measurement recorded. This measurement will be repeated twice, 20 seconds apart. If the two measurements differ by >10%, a third measurement will be recorded, with the closest two readings kept and the outlier discarded. If TetraGraph yields a train-of-four count but not a ratio with any measurement, this will be recorded.
- To obtain ToFscan measurements, TOF stimulation will be performed and the measurement recorded. According to the manufacturer, the ToFscan does not require calibration, and the default stimulating current is 50 mA. The TOF measurement will be repeated twice, 20 seconds apart. If the measurements differ by >10%, a third measurement will be repeated, with the closest two readings kept and the outlier discarded. If TetraGraph yields a train-of-four count but not a ratio with any measurement, this will be recorded.

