10.2 Statistical Methods

Descriptive Statistics

Analysis of agreement between the devices will be assessed using the method described by Bland and Altman (Olofson et al. 2015). The bias is defined as the mean difference of repeated measurements from the ToFscan and the TetraGraph obtained at the same time intervals. The limits of agreement are defined as $\text{bias} \pm 2 \text{ SD}$, where SD denotes the standard deviations of the differences. Limits of agreement are interpreted as the reference range within which 95% of the differences will lie. The bias and the limits of agreements surrounding the bias ($\pm 2 \text{ SD}$) will be calculated with 95% confidence intervals. Repeatability between the two devices at the various time intervals will also be assessed with significance defined as a p-value <0.05 .

Handling of Missing Data

This is a prospective study and therefore we do not anticipate any missing data. In the event of any unexpected missing data, no attempt to impute this missing data will be made; missing data will simply be treated as missing in the statistical analysis.

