18.3 PACU data

Study ID	
Date of Surgery (dd / mm / yyyy):	

Initials:		Dominant side:	L / R	Age (yrs):	
Weight (kg):		Height (cm):		BMI:	

TetraGraph (TG)

Arm tested: dominant / non-dominant

	TOFR #1	TOFR #2	TOFR #3 (if needed)	VNRS
T0 (on arrival to PACU)				
T5 (5 min later)				
T10 (10 min later)				
Predischarge VNRS	xxx	xxx	xxx	

ToFscan (TS)

Arm tested: -dominant / non-dominant

	TOFR #1	TOFR #2	TOFR #3 (if needed)	VNRS
T0 (on arrival to PACU)				
T5 (5 min later)				
T10 (10 min later)				
Predischarge VNRS	xxx	xxx	xxx	

TG= TetraGraph; TS= ToFscan; TOFR= train-of-four ratio; VNRS= verbal numeric rating scale

19 List of In-Text Figures

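### Repeatability is the primary endpoint in 6.4, but 10.2 plans no estimate of it for either device, and the reading rule in 9.2 would by default make such an estimate too small

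*Combined protocol and SAP*

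**What the plan says.** The protocol uses the term repeatability in four places and defines it in none.

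- Section 6.4: "The primary endpoint of the study will be the repeatability of values obtained by ToFscan and TetraGraph monitors".
- Synopsis, Objectives: "The primary aim of this study is to assess the agreement and repeatability between TOF values obtained from ToFscan and TetraGraph".
- Section 5, primary objective: "To assess the agreement and repeatability between TOF values obtained from the ToFscan and TetraGraph during recovery from neuromuscular blockade".
- Section 10.2: "Repeatability between the two devices at the various time intervals will also be assessed with significance defined as a p-value" below 0.05.

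Section 10.2 treats agreement in more detail. It cites a Bland-Altman method and defines the bias ("The bias is defined as the mean difference of repeated measurements from the ToFscan and the TetraGraph obtained at the same time intervals"), with limits at 2 SD either side and 95% confidence intervals.

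Section 9.2 has each device read twice, 20 seconds apart, at each of three time points. If the two readings differ by more than 10%, the TetraGraph rule is "a third measurement will be recorded, with the closest two readings kept and the outlier discarded"; the ToFscan rule is the same. The PACU data form (18.3) has columns for all three readings. The synopsis describes the purpose: "This pilot study is meant to be descriptive and it aims to collect basic data for future larger study".

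**The concern.** The endpoint named in 6.4 has the thinnest analysis in the plan: a significance threshold with no named test, hypothesis or estimand. A p-value alone would not tell the planners of a larger study how repeatable either monitor is. The rationale makes this a live question, since the introduction argues that movement in awakening patients can make acceleromyography readings inaccurate while electromyography is unaffected.

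The second problem is how an analyst would fill the gap. The rule in 9.2 selects readings by how closely they agree, which is the quantity repeatability measures. Followed as written, it makes a device look more repeatable than it is, and more so for the noisier device.

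**Working it through.** **1. Is there a planned figure to reproduce?** Not for repeatability. The only calculation is in 10.1: 23 patients, paired t-test, 90% power, significance level 0.05, SD 0.07, with no stated difference. An assumed difference of 0.05 (two-sided, 0.07 as the SD of differences) gives n = 23 with 90.5% power. That concerns a mean between-device difference and says nothing about repeatability.

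**2. Can the Bland-Altman limits stand in?** For single readings, the variance of the between-device difference is s_w(TetraGraph)² + s_w(ToFscan)² + τ², where τ² covers differences between arms and patient-specific bias. Take τ = 0. Values of 0.06 and 0.03 give √(0.06² + 0.03²) = 0.067, so limits of bias ± 0.134. Exchanging the two devices gives the same limits. They cannot show which device repeats less well.

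**3. What does the 9.2 rule do to s_w?** Inputs from 9.2: two readings, a third if they differ by more than 10%, closest two kept. Assumptions, because the documents give no values: independent normal errors, mean ratio 0.95, and 10% taken relative to the mean of #1 and #2. The chance of a third reading is approximately 2[1 − Φ(0.095 / (√2·s_w))]; at s_w = 0.05 this is 2[1 − Φ(1.34)] ≈ 18%. The kept-reading s_w is √(mean(d²)/2), with d the difference of the kept pair, from 2,000,000 simulated triplets per setting.

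| True s_w | Third reading needed | Kept s_w / true, relative 10% | Kept s_w / true, absolute 0.10 |
|---|---|---|---|
| 0.02 | 0.1% | 0.995 | 0.998 |
| 0.03 | 2.5% | 0.92 | 0.94 |
| 0.05 | 18% | 0.67 | 0.70 |
| 0.07 | 34% | 0.53 | 0.55 |
| 0.10 | 50% | 0.45 | 0.46 |

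For means from 0.70 to 1.00 (relative rule) the ratios run 0.95–1.00, 0.78–0.94, 0.54–0.70, 0.46–0.55 and 0.43–0.46. Using #1 and #2 throughout returns a ratio of 1.00.

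On the scale of the repeatability coefficient, 1.96·√2·s_w: at s_w = 0.05 the true value is 0.139, and the kept readings give 0.139 × 0.67 = 0.093.

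**4. Is this larger than sampling error?** With 120 patients and 3 pairs each (360 degrees of freedom, equal s_w across patients), the 95% interval for s_w is −7% to +8%; it is wider if s_w varies between patients. From about 0.05 upward the selection effect is the larger of the two.

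**5. Does it affect agreement?** The mean of the kept pair shifts by less than 0.001, so the bias is essentially untouched. The SD of that mean is about 2% to 13% larger than for the mean of #1 and #2 over s_w 0.03 to 0.10, so the replicate part of the limits changes a little.

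**6. Is the device contrast compressed?** Suppose the true ratio of the two s_w is 2.0, and that 0.07 is the SD of single-reading differences. If 0%, 25%, 50% or 75% of 0.07² comes from sources other than replicate noise, the kept readings give a ratio of 1.26, 1.33, 1.48 or 1.81.

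**The case against.** **Repeatability may have been meant loosely.** The synopsis, section 5 and 10.2 all phrase it as something between the two devices; only 6.4 does not. Duplicate readings make a within-device estimate feasible but do not prove it was intended. This stands. If only agreement was meant, the calculation in step 3 falls away and a terminology fault remains. The text needs changing either way.

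**Section 9.2 does say what happens to the outlier.** It is discarded, which ordinarily means not analysed. This also stands: the plan is not silent, and kept readings are the default. The gap is that 10.2 makes no exception for the one analysis where that default distorts the result.

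**Discarding may be sensible when patients move.** As an assumed illustration, take base s_w 0.02 with 5% of readings carrying artefact of SD 0.2. Readings #1 and #2 then give 0.049 and the kept readings 0.022. The kept figure is close to artefact-free repeatability; the unfiltered one includes what a user would meet in the PACU. They answer different questions, so both should be shown.

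**It is a descriptive pilot.** True, but a descriptive study calls for an estimate per device more than for a p-value.

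A reader might also infer that the difference between the devices will be largely hidden. The documents do not support that. The 0.07 comes from volunteers and another acceleromyography device, its replicate share is unknown, and step 6 runs from strong compression to little.

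**Conclusion.** The point holds and should be fixed. The gap in specification is certain from the text: the endpoint in 6.4 has no definition, no named test and no planned estimate for either device in 10.2. What the cited Bland-Altman reference contains cannot be checked here, but it is cited for agreement and the protocol text takes no within-device component from it.

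The size of the selection effect is conditional. It requires that repeatability be read as within-device, that the kept readings be used, and that errors be roughly normal. It is negligible near s_w 0.02, about 8% at 0.03, about a third at 0.05 and more than half at 0.10. Those s_w values are assumptions.

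It would go too far to conclude that the study will report a biased repeatability figure, since 10.2 plans no such figure, or that the agreement analysis is undermined, since the bias is essentially unaffected.

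**What to change.** In 10.2, replace the repeatability sentence with wording such as: *Repeatability is the within-device variation of readings taken 20 seconds apart. For each device, s_w and the repeatability coefficient 1.96·√2·s_w are estimated from readings #1 and #2, before any reading is discarded, with 95% confidence intervals that account for clustering by patient. The devices are compared by the ratio of the two SDs with a 95% confidence interval. The same quantities from the kept readings are reported alongside.*

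Also state:

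- which readings enter the Bland-Altman analysis;
- whether the 10% trigger is absolute or relative;
- that measurements giving a count but no ratio are reported as a number per device and left out of s_w.

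Align 6.4 with section 5 by naming agreement and within-device repeatability. If only between-device agreement was meant, say so in 6.4 and remove the repeatability sentence from 10.2.

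The cost is wording: no added patients, visits or readings, since the form in 18.3 already holds all three values. The drawback is that the unfiltered s_w includes movement artefact and will look less favourable; the kept figure excludes discordant readings by construction. Showing both lets the reader see the difference.

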10.3 Subject Population(s) for Analysis

Each participant who goes through the recovery processes in the PACU and completes monitoring of residual neuromuscular blockade will be included in the primary analysis regardless of study withdrawal for any reason. In the event of any study withdrawals, in secondary analysis we will examine the sensitivity of our results to the exclusion of patients who withdrew.

11 Safety and Adverse Events

11.1 Definitions

11.1.1 Unanticipated Problems Involving Risk to Subjects or Others (UPIRTSO)

Any unanticipated problem or adverse event that meets the following three criteria:

- Serious: Serious problems or events that results in significant harm, (which may be physical, psychological, financial, social, economic, or legal) or increased risk for the subject or others (including individuals who are not research subjects). These include: (1) death; (2) life threatening adverse experience; (3) hospitalization - inpatient, new, or prolonged; (4) disability/incapacity - persistent or significant; (5) birth defect/anomaly; (6) breach of confidentiality and (7) other problems, events, or new information (i.e. publications, DSMB reports, interim findings, product labeling change) that in the opinion of the local investigator may adversely affect the rights, safety, or welfare of the subjects or others, or substantially compromise the research data, **AND**
- Unanticipated: (i.e. unexpected) problems or events are those that are not already described as potential risks in the protocol, consent document, or not part of an underlying disease. A problem or event is "unanticipated" when it was unforeseeable at the time of its occurrence. A problem or event is "unanticipated" when it occurs at an increased frequency or at an increased severity than expected, **AND**
- Related: A problem or event is "related" if it is possibly related to the research procedures.

11.1.2 Adverse Event

An untoward or undesirable experience associated with the use of a medical product (i.e. drug, device, biologic) in a patient or research subject.

11.1.3 Serious Adverse Event

Adverse events are classified as serious or non-serious. Serious problems/events can be well defined and include;

- death
- life threatening adverse experience
- hospitalization
- inpatient, new, or prolonged; disability/incapacity
- persistent or significant disability or incapacity
- birth defect/anomaly

and/or per protocol may be problems/events that in the opinion of the sponsor-investigator may have adversely affected the rights, safety, or welfare of the subjects or others, or substantially compromised the research data.

All adverse events that do not meet any of the criteria for serious, should be regarded as **non-serious adverse events**.

11.1.4 Adverse Event Reporting Period

For this study, the follow-up period is defined as 10 minutes following the arrival in the PACU.

11.1.5 Preexisting Condition

A preexisting condition is one that is present at the start of the study. A preexisting condition should be recorded as an adverse event if the frequency, intensity, or the character of the condition worsens during the study period.

11.1.6 Post-study Adverse Event

All unresolved adverse events should be followed by the sponsor-investigator until the events are resolved, the subject is lost to follow-up, or the adverse event is otherwise explained. At the last scheduled visit, the sponsor-investigator should instruct each subject to report, to the sponsor-investigator, any subsequent event(s) that the subject, or the subject's personal physician, believes might reasonably be related to participation in this study.

11.1.7 Hospitalization, Prolonged Hospitalization or Surgery

Any adverse event that results in hospitalization or prolonged hospitalization should be documented and reported as a serious adverse event unless specifically instructed otherwise in this protocol. Any condition responsible for surgery should be documented as an adverse event if the condition meets the criteria for an adverse event.

Neither the condition, hospitalization, prolonged hospitalization, nor surgery are reported as an adverse event in the following circumstances:

- Hospitalization or prolonged hospitalization for therapy of the target disease of the study, unless it is a worsening or increase in frequency of hospital admissions as judged by the clinical investigator.

11.2 Recording of Adverse Events

At each contact with the subject, the study team must seek information on adverse events by specific questioning and, as appropriate, by examination. Information on all adverse events should be recorded immediately in the source document, and also in the appropriate adverse event section of the electronic case report form (CRF). All clearly related signs, symptoms, and abnormal diagnostic, laboratory or procedure results should be recorded in the source document.

All adverse events occurring during the study period must be recorded. The clinical course of each event should be followed until resolution, stabilization, or until it has been ultimately determined that the study treatment or participation is not the probable cause. Serious adverse

events that are still ongoing at the end of the study period must be followed up, to determine the final outcome. Any serious adverse event that occurs during the Adverse Event Reporting Period and is considered to be at least possibly related to the study treatment or study participation should be recorded and reported immediately.

11.3 Reporting of Serious Adverse Events and Unanticipated Problems

When an adverse event has been identified, the study team will take appropriated action necessary to protect the study participant and then complete the Study Adverse Event Worksheet and log. The sponsor-investigator will evaluate the event and determine the necessary follow-up and reporting required.

11.3.1 Sponsor-Investigator reporting: notifying the Mayo IRB

The sponsor-investigator will report to the Mayo IRB any UPIRTSOs and Non-UPIRTSOs according to the Mayo IRB Policy and Procedures. Each participating site will report SAEs to their respective IRB or Ethics Committee with copy of submission and review provided to the leading site. Should there be any SAEs at any of the participating sites; the study team at that site will notify the primary site (Mayo Clinic in Florida) within 24 hours of learning of the event.

Any serious adverse event (SAE) which the Principal Investigator has determined to be a UPIRTSO will be reported to the Mayo IRB as soon as possible but no later than 5 working days after the investigator first learns of the problem/event.

The following information will be collected on the adverse event worksheet (and entered in the research database):

- Study ID
- Disease
- The date the adverse event occurred
- Description of the adverse event
- Relationship of the adverse event to the research device*
- Determination if the adverse event was expected
- The severity of the adverse event (severity scale described below**)
- If any intervention was necessary
- Resolution (was the incident resolved spontaneously, or after discontinuing treatment)
- Date of Resolution

The sponsor-investigator will review all adverse event reports to determine if specific reports need to be made to the IRB. The sponsor-investigator will sign and date the adverse event report when it is reviewed. For this protocol, only directly related SAEs/UPIRTSOs will be reported to the IRB.

*** Relationship Index**

The relationship of an AE to the Investigational Device is a clinical decision by the sponsor-investigator (PI) based on all available information at the time of the completion of the eCRF and is graded as follows:

1. Not related: a reaction for which sufficient information exists to indicate that the etiology is unrelated to the use and proper application of study device.
2. Unlikely: a clinical event, including laboratory test abnormality, with a temporal relationship to use of the study device which makes a causal relationship improbable and in which use of other devices, chemicals, or underlying disease provide plausible explanations.
3. Possible: a clinical event, including laboratory test abnormality, with a reasonable time sequence to use of the study device but which could also be explained by concurrent disease or use of other devices or chemicals.
4. Probable: a clinical event including laboratory test abnormality, with a reasonable time sequence to use of the study device, unlikely to be attributed to concurrent disease or use of other devices or chemicals.
5. Definite: a reaction that follows a reasonable temporal sequence from the use of the study device.

